2.2.2.2 Safety and tolerability

Safety and tolerability of the treatments will be assessed based on:

- Adverse events (including clinically relevant findings from the physical examination)
- Safety laboratory tests
- 12-lead ECG
- Vital signs (body temperature, blood pressure, pulse rate)

3. DESCRIPTION OF DESIGN AND TRIAL POPULATION

3.1 OVERALL TRIAL DESIGN AND PLAN

The study will be performed as an open-label, two-treatment, two-period, fixed sequence design trial in healthy male subjects in order to compare the test treatment (T) to the reference treatment (R). The treatments will be one oral single dose of [REDACTED] BI 706321 administered as tablet formulation together with multiple oral doses of 200 mg itraconazole as oral solution formulation (concentration: 10 mg/mL) (treatment T) and one single dose of [REDACTED] BI 706321 as tablet given alone (R).

In both treatments, BI 706321 is administered to subjects in the fasting state. In the first treatment period (Period 1, Visit 2), all subjects are planned to undergo treatment R, and in the second treatment period (Period 2, Visit 3), all subjects are planned to undergo treatment T. For details, refer to Section [4.1](#).

There will be a washout period of at least 14 days between the administrations of BI 706321.

[figure not shown]

Figure 3.1: 1

Trial design

An overview of all relevant trial activities is provided in the [Flow Chart](#). For visit schedule and details of trial procedures at selected visits, refer to Sections [6.1](#) and [6.2](#), respectively.

3.2 DISCUSSION OF TRIAL DESIGN, INCLUDING THE CHOICE OF CONTROL GROUPS

For drug interaction trials, the crossover design is preferred because of its efficiency: since each subject serves as his/her own control, the comparison between treatments is based on an intra-subject comparison, thus removing inter-subject variability from the comparison between treatments [\[R94-1529\]](#).

Because of the long half-life (about 40 h) of itraconazole and its metabolites, a two-period fixed sequence design was selected, with administration of itraconazole in the second study period only. This design is not expected to lead to systematic errors in the estimation of the treatment effects since nonspecific time-effects are unlikely due to the short trial duration. For itraconazole studies, this design is recommended by the Innovation and Quality in

Proprietary confidential information © 2021 Boehringer Ingelheim International GmbH or one or more of its affiliated companies

Pharmaceutical Development's [REDACTED] [R17-3744].

For this PK drug-drug interaction trial, open-label treatment is acceptable, because the primary and secondary endpoints of this trial are PK endpoints derived from measurement of plasma concentrations of BI 706321. These endpoints are not expected to be affected by knowledge of treatment.

3.3 SELECTION OF TRIAL POPULATION

It is planned that 14 healthy male subjects will enter the study. They will be recruited from the volunteers' pool of the trial site.

Due to the reproduction toxicity itraconazole has shown in nonclinical studies, only male subjects will be included in this trial.

A log of all subjects enrolled into the trial (i.e. who have signed informed consent) will be maintained in the ISF irrespective of whether they have been treated with investigational drug or not.

3.3.1 Main diagnosis for trial entry

The study will be performed in healthy subjects.

3.3.2 Inclusion criteria

Subjects will only be included in the trial if they meet the following criteria:

1. Healthy male subjects according to the assessment of the investigator, as based on a complete medical history including a physical examination, vital signs (body temperature, BP, PR), 12-lead ECG, and clinical laboratory tests
2. Age of 18 to 50 years (inclusive)
3. BMI of 18.5 to 29.9 kg/m² (inclusive)
4. Signed and dated written informed consent prior to admission to the study, in accordance with GCP and local legislation

3.3.3 Exclusion criteria

Subjects will not be allowed to participate, if any of the following general criteria apply:

1. Any finding in the medical examination (including BP, PR or ECG) deviating from normal and assessed as clinically relevant by the investigator
2. Repeated measurement of systolic blood pressure outside the range of 90 to 140 mmHg, diastolic blood pressure outside the range of 50 to 90 mmHg, or pulse rate outside the range of 45 to 90 bpm
3. Any laboratory value outside the reference range that the investigator considers to be of clinical relevance
4. Any evidence of a concomitant disease assessed as clinically relevant by the investigator

Proprietary confidential information © 2021 Boehringer Ingelheim International GmbH or one or more of its affiliated companies

5. Gastrointestinal, hepatic, renal, respiratory, cardiovascular, metabolic, immunological or hormonal disorders
6. Cholecystectomy or other surgery of the gastrointestinal tract that could interfere with the pharmacokinetics of the trial medication (except appendectomy or simple hernia repair)
7. Diseases of the central nervous system (including but not limited to any kind of seizures or stroke), and other relevant neurological or psychiatric disorders
8. History of relevant orthostatic hypotension, fainting spells, or blackouts
9. Relevant chronic or acute infections
10. History of relevant allergy or hypersensitivity (including allergy to the trial medication or its excipients)
11. Use of drugs within 30 days of planned administration of trial medication that might reasonably influence the results of the trial (including drugs that cause QT/QTc interval prolongation)
12. Intake of an investigational drug in another clinical trial within 60 days of planned administration of investigational drug in the current trial, or concurrent participation in another clinical trial in which investigational drug is administered
13. Smoker (more than 10 cigarettes or 3 cigars or 3 pipes per day)
14. Inability to refrain from smoking on specified trial days
15. Alcohol abuse (consumption of more than 24 g per day) and unwillingness/inability to refrain from intake of alcoholic beverages from 48 hours prior to first trial medication administration and until 7 days post last trial medication administration
16. Drug abuse or positive drug screening
17. Blood donation of more than 100 mL within 30 days of planned administration of trial medication or intended blood donation during the trial
18. Intention to perform excessive physical activities within one week prior to the administration of trial medication or during the trial
19. Inability to comply with the dietary regimen of the trial site
20. A marked prolongation of QT/QTc interval (such as QTc intervals that are repeatedly greater than 450 ms) or any other relevant ECG finding at screening
21. A history of additional risk factors for *Torsade de Pointes* (such as heart failure, hypokalaemia, or family history of Long QT Syndrome)
22. Subject is assessed as unsuitable for inclusion by the investigator, for instance, because the subject is not considered able to understand and comply with study requirements, or has a condition that would not allow safe participation in the study
23. Liver enzymes (ALT, AST, GGT) above upper limit of normal at the screening examination, confirmed by a repeat test
24. History of drug induced liver injury
25. History of heart failure, or any evidence of ventricular dysfunction
26. Known sorbitol/polyols intolerance
27. During COVID-19 pandemic: laboratory test indicative of an ongoing SARS-CoV-2 infection

For study restrictions, refer to Section [4.2.2](#).

3.3.4 Withdrawal of subjects from treatment or assessments

Subjects may discontinue trial treatment or withdraw consent to trial participation as a whole ('withdrawal of consent') with very different implications; please see sections [3.3.4.1](#) and [3.3.4.2](#) below.

If a subject is removed from or withdraws from the trial prior to the first administration of trial medication, the data of this subject will not be entered in the case report form (CRF) and will not be reported in the clinical trial report (CTR). If a subject is removed from or withdraws from the trial after the first administration of trial medication, this will be documented and the reason for discontinuation must be recorded in the CRF; in addition, the data will be included in the CRF and will be reported in the CTR. At the time of discontinuation, a complete end of trial examination will be performed, if possible, and the information will be recorded in the CRF. If the discontinuation occurs before the end of the REP (see Section [1.2.3](#)), the discontinued subject should if possible be questioned for AEs and concomitant therapies at or after the end of the REP in order to ensure collection of AEs and concomitant therapies throughout the REP, if not contrary to any consent withdrawal of the subject.

3.3.4.1 Discontinuation of trial treatment

An individual subject will discontinue trial treatment if:

1. The subject wants to discontinue trial treatment, without the need to justify the decision
2. The subject has repeatedly shown to be non-compliant with important trial procedures and, in the opinion of both, the investigator and sponsor representative, is not willing or able to adhere to the trial requirements in the future.
3. The subject needs to take concomitant medication that interferes with the investigational medicinal product or other trial treatment
4. The subject can no longer receive trial treatment for medical reasons (such as surgery, adverse events [AEs], or diseases)
5. An AE or clinically significant laboratory change or abnormality occurs that the investigator assesses as warranting discontinuation of treatment. This may include:
 - The subject has an elevation of AST and/or ALT ≥ 3 -fold ULN
 - The subject has a serious adverse reaction or a severe non-serious adverse reaction
6. The subject has an elevation of AST and/or ALT ≥ 3 -fold ULN and an elevation of total bilirubin ≥ 2 -fold ULN (measured in the same blood sample) and/or needs to be followed up according to the DILI checklist provided in the ISF

In addition to these criteria, the investigator may discontinue subjects at any time based on his or her clinical judgment.

Even if the trial treatment is discontinued, the subject remains in the trial and, given his/her agreement, will undergo the procedures for early treatment discontinuation and follow up as outlined in the [Flow Chart](#) and section [6.2.3](#).

Proprietary confidential information © 2021 Boehringer Ingelheim International GmbH or one or more of its affiliated companies

3.3.4.2 Withdrawal of consent to trial participation

Subjects may withdraw their consent to trial participation at any time without the need to justify the decision. If a subject wants to withdraw consent, the investigator should be involved in the discussion with the subject and explain the difference between trial treatment discontinuation and withdrawal of consent to trial participation, as well as explain the options for continued follow up after trial treatment discontinuation, please see section [3.3.4.1](#) above

3.3.4.3 Discontinuation of the trial by the sponsor

Boehringer Ingelheim reserves the right to discontinue the trial at any time for any of the following reasons:

1. Failure to meet expected enrolment goals overall or at a particular trial site
2. New toxicological findings, serious adverse events, or any safety information invalidating the earlier positive benefit-risk-assessment. More specifically, the trial will be terminated if more than 50% of the subjects have drug-related and clinically relevant adverse events of moderate or severe intensity, or if at least 1 drug-related serious adverse event is reported
3. Violation of GCP, or the CTP, or the contract with BI impairing the appropriate conduct of the trial
4. The sponsor decides to discontinue the further development of the investigational product

The investigator / trial site will be reimbursed for reasonable expenses incurred in case of trial termination (except if item 3 applies).

3.3.5 Replacement of subjects

Subjects withdrawn due to drug related adverse events will not be replaced. In case more than 2 subjects do not complete the trial, the Clinical Trial Leader together with the Trial Pharmacokineticist and the Trial Statistician are to decide, if and how many subjects will be replaced. A replacement subject will be assigned a unique trial subject number.

4. TREATMENTS

4.1 INVESTIGATIONAL TREATMENTS

The investigational product BI 706321 as tablet formulation will be supplied by BI Pharma GmbH & Co. KG.

Itraconazole oral solution will be obtained from a public pharmacy.

4.1.1 Identity of the Investigational Medicinal Products

The characteristics of the trial products are given below:

Trial product 1

Substance: BI 706321
Pharmaceutical formulation: Tablet, film-coated
Source: BI Pharma GmbH & Co. KG, Germany
Unit strength: 
Posology: 1-0-0
Route of administration: Oral
Duration of use: Single dose in treatments R and T

Trial product 2

Name: Sempera® Liquid 10 mg/mL
Substance: Itraconazole
Pharmaceutical formulation: Oral solution
Source: Public pharmacy
Holder of marketing authorisation: 
Unit strength: 10 mg/mL
Posology: 20 mL-0-0
Route of administration: Oral
Duration of use: 14 days in treatment T

4.1.2 Selection of doses in the trial

Perpetrator (itraconazole)

The dose of itraconazole selected for this trial reflects standard clinical doses, is considered sufficient to yield significant CYP3A and P-gp inhibition and has been used successfully and safely in previous drug-drug-interaction trials ([c02336088](#), [c03355329](#), [c08928447](#)).

Proprietary confidential information © 2021 Boehringer Ingelheim International GmbH or one or more of its affiliated companies

Victim (BI 706321)

Based on *in vitro* data, CYP3A is the major CYP isoform responsible for the metabolism of BI 706321. Additionally, BI 706321 is an *in vitro* substrate of P-gp. Thus, concomitant administration of BI 706321 with the strong CYP3A inhibitor itraconazole may result in substantial increases of BI 706321 plasma concentrations.

For the current trial, a dose of [REDACTED] BI 706321 is selected, in order to ensure that BI 706321 plasma concentrations, even in case of a substantial increase when given with itraconazole, are within the range of concentrations that were explored in the SRD part of trial 1425-0001 and that were associated with good safety and tolerability (ref. Section [1.2.1](#)).

4.1.3 Method of assigning subjects to treatment groups

There is only one treatment sequence investigated in this trial, and each subject will be allocated to the same treatment sequence (R-T). The subjects will be allocated to a study subject number by the method “first come-first served” prior to first administration of trial medication in the morning of Day 1 of Visit 2. Once a subject number has been assigned, it cannot be reassigned to any other subject.

All subjects may be treated in one cohort, i.e. all subjects may receive treatment on the same calendar day. In case this is not feasible (e.g., due to logistical or recruitment reasons), the group may be split into several cohorts as required.

Treatment of all subjects on the same calendar day is acceptable (for safety margin to exposure reached in previous SRD trial 1425-0001 refer to Section [1.4.2.1.1](#); for discussion of study-associated risks and safety measures see Section [1.4](#)).

4.1.4 Drug assignment and administration of doses for each subject

The treatments to be evaluated are outlined in Table [4.1.4: 1](#) below. All subjects will receive the 2 treatments in a fixed order.

Table 4.1.4: 1 Dosage and treatment schedule

Treatment period	Treatment	Substance	Formulation	Unit strength	Dosage	Total dose
1	R (Reference)	BI 706321	Tablet, film-coated	[REDACTED]	1 tablet as single dose (Day 1)	[REDACTED]
2	T (Test)	BI 706321	Tablet, film-coated	[REDACTED]	1 tablet as single dose (Day 1)	[REDACTED]
		Itraconazole	Oral solution	10 mg/mL	20 mL (200 mg) qd for 14 days (Days -3 to 11)	2800 mg

Administration of trial medication will be performed after subjects have fasted overnight; fasting is to start no later than 10 h before the scheduled dosing of BI 706321 or 9 hours before itraconazole administration. The investigator (or authorised designee) will administer the trial medication as an oral dose together with about 240 mL of water to subjects who are in a standing or sitting position. For drug administration, the so-called four-eye principle (two-person rule) should be applied. For this, one authorised employee of the trial site should

Proprietary confidential information © 2021 Boehringer Ingelheim International GmbH or one or more of its affiliated companies

witness the administration of trial medication, and – if applicable – its preparation (e.g. reconstitution), if correct dosage cannot be ensured otherwise.

Subjects will be kept under close medical surveillance until at least 24 hours and 46 hours after administration of BI 706321 in Visit 2 and Visit 3, respectively. During the first 4 h after administration of BI 706321, subjects are not allowed to lie down (i.e. no declination of the upper body of more than 45 degrees from upright posture).

The treatments with BI 706321 will be separated by a wash-out phase of at least 14 days.

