1.2.2 Itraconazole

Absorption of itraconazole solution is fast with maximum plasma concentration being reached within 2.5 h after oral administration in fasting condition. Bioavailability of itraconazole liquid increases by 30% when given under fasting condition compared to administration together with food [R20-2709]. Mean peak plasma concentrations were 547.7 ng/mL after a single dose of 200 mg itraconazole solution (fasting) and 1965 ng/mL after 15 days of daily treatment with 200 mg itraconazole solution (fasting). Pharmacokinetics of itraconazole is non-linear. The half-life of itraconazole after multiple doses of 200 mg once daily with solution formulation was about 40 h [R17-3742].

In the liver, itraconazole is metabolised extensively to more than 30 metabolites [R17-3743]. Its main metabolite, hydroxy-itraconazole, accounts for about twice the concentration of plasma itraconazole at trough. It has been shown *in vitro* that CYP3A4 is mainly responsible for the formation of this metabolite [R20-2709]. FDA classifies itraconazole as strong index inhibitor of CYP3A and as inhibitor of P-glycoprotein (P-gp) [R18-0241]. However, not only itraconazole contributes to the *in vivo* inhibition of CYP3A observed after itraconazole administration but also three of its metabolites (hydroxy-itraconazole, keto-itraconazole, and N desalkyl-itraconazole) [R10-1102].

For a more detailed description of itraconazole, please refer to the German Summary of Product Characteristics (SmPC) for Sempera® Liquid 10 mg/ml [R20-2709].

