1.2.3 Residual Effect Period

The Residual Effect Period (REP, i.e., the period after the last dose with measurable drug levels and/or pharmacodynamic effects still likely to be present) of BI 706321 is assumed to be 8 days, i.e. based on [redacted] terminal $t_{1/2}$ seen in the FIH trial 1425-0001.

When given together with itraconazole (Treatment T), it is expected that plasma exposure of BI 706321 could be increased (albeit within the exposures explored in the clinical trial 1425-0001), and the time of relevant plasma exposure could be prolonged. This might result in a prolonged period in which adverse effects could potentially occur.

For the use of itraconazole in Treatment T, the REP is defined as 8 days after last administration of itraconazole on Day 11 in Period 2.

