1.3 RATIONALE FOR PERFORMING THE TRIAL

Based on *in vitro* data, BI 706321 is mainly metabolized via CYP 3A4. Additionally, BI 706321 is an *in vitro* substrate of P-glycoprotein (P-gp).

Therefore, in this trial, the focus is on the drug-drug interaction (DDI) victim potential of BI 706321 with regard to CYP3A4 and P-gp as this may lead to clinically relevant increases in exposures with potential impact on patient safety.

Itraconazole is chosen for this trial as perpetrator drug, as this drug is recommended as strong inhibitor of CYP3A by EMA and PMDA [[P15-06991](#), [P15-06298](#)], and as strong index inhibitor of CYP3A and P-gp by FDA [[R18-0241](#)].

Moreover, safety and tolerability of itraconazole were acceptable in previous DDI trials [[c02336088](#), [c03355329](#), [c08928447](#)].

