1.4.2.4 Potential drug-drug interaction between BI 706321 and itraconazole

It is likely that concomitant administration of BI 706321 with itraconazole leads to an increase of plasma concentrations and terminal half-life of BI 706321. The effect of itraconazole in increasing C_{max} and AUC of other drugs can be as high as 3.4-fold and 11-fold, respectively, as seen with oral midazolam, a sensitive CYP3A4 substrate, when co-administered with oral itraconazole 200 mg/d [[R01-0516](#), [R20-2709](#)].

Proprietary confidential information © 2021 Boehringer Ingelheim International GmbH or one or more of its affiliated companies

Inhibition of P-gp may increase exposure of sensitive P-gp substrates like fexofenadine by factor 3-4 [[R08-1652](#), [P07-13746](#)] and increase digoxin exposure by ~1.7-fold [[R15-3252](#)]. Therefore, a low dose of [REDACTED] BI 706321 has been selected for this trial (see Section [4.1.2](#)) to ensure that BI 706321 plasma concentrations, even in case of a substantial increase when given with itraconazole, [REDACTED] and that were associated with good safety and tolerability (ref. Section [1.2.1](#)).

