2. TRIAL OBJECTIVES AND ENDPOINTS

2.1 MAIN OBJECTIVES, PRIMARY AND SECONDARY ENDPOINTS

2.1.1 Main objectives

The main objective of this trial is to investigate the effect on the exposure of BI 706321 in plasma when given as oral single dose together with multiple oral doses of itraconazole (Test, T) as compared to when given alone as oral single dose (Reference, R).

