2.1.3 Secondary endpoint

The following pharmacokinetic parameter will be determined for BI 706321:

- AUC_{0-tz} (area under the concentration-time curve of the analyte in plasma over the time interval from 0 to the last quantifiable data point)

Proprietary confidential information © 2021 Boehringer Ingelheim International GmbH or one or more of its affiliated companies

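### Does stopping itraconazole on Day 11, before treatment T sampling ends, make the AUC0-∞ ratio misleading?

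*Protocol*

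**What the plan says.** Protocol Table 4.1.4: 1 gives the itraconazole schedule as "20 mL (200 mg) qd for 14 days (Days -3 to 11", total 2800 mg. The Flow Chart puts BI 706321 on the fourth itraconazole day and the last itraconazole dose at 238 h. Treatment T samples follow at 262, 310, 358, 406, 454, 502 and 550 h.

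Protocol 2.1.1 sets the objective: "investigate the effect on the exposure of BI 706321 in plasma when given as oral single dose together with multiple oral doses of itraconazole". The comparator is BI 706321 alone. The rationale in Protocol 1.3 is broader: "the focus is on the drug-drug interaction (DDI) victim potential of BI 706321 with regard to CYP3A4 and P-gp". Protocol 1.4.2.4 considers it likely that the combination "leads to an increase of plasma concentrations and terminal half-life of BI 706321".

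On the inhibitor, Protocol 1.2.2 says: "The half-life of itraconazole after multiple doses of 200 mg once daily with solution formulation was about 40 h". Section 3.2 applies the same figure to the metabolites: "Because of the long half-life (about 40 h) of itraconazole and its metabolites". The half-life of BI 706321 is blacked out. Protocol 1.2.3 shows only that its residual effect period "of BI 706321 is assumed to be 8 days, i.e. based on" a redacted quantity.

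SAP 7.4 and 7.4.1 analyse AUC0-∞ and Cmax with a mixed model on the log scale and report T/R ratios with 90% confidence intervals. The visible SAP text says nothing about inhibition fading inside the AUC0-∞ window.

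**The concern.** AUC0-∞ collects the whole concentration curve, but the inhibitor is present at full strength for only part of it. If BI 706321 lasts longer with itraconazole, as the protocol expects, late samples may be taken while clearance is returning to normal. AUC0-∞ under T is then smaller than it would be had itraconazole continued.

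Protocol 7.2 sets no acceptance range, so the size of the ratio is itself the result. Someone reading Protocol 1.3 could take that ratio as the effect of continuous strong CYP3A4 and P-gp inhibition. If systemic clearance is inhibited, that reading is too low, and it errs towards understating exposure. A supportive analysis, or a caveat written into the SAP, might therefore seem to be needed.

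**Working it through.** **The plan's own figures.** Days -3 to -1 give 3 doses and Days 1 to 11 give 11. That is 14 doses, and 14 × 200 mg = 2800 mg, as stated.

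The precision in Protocol Table 7.7: 1 (N = 12, 95% probability) follows from

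exp{ t(0.95; 11) × √(2/12) × √ln(1 + gCV²) × √(χ²(0.95; 11)/11) }

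with t = 1.796 and χ² = 19.675. At gCV 20%, 25% and 30% it gives 1.214, 1.273 and 1.334, matching the printed 1.21, 1.27 and 1.33.

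**Inhibitor left at the late samples.** The fraction is 2^(−Δ/40), with Δ counted from the last dose (238 h) or from the end of its dosing interval (262 h).

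| Sample | From 238 h | From 262 h |
|---|---|---|
| 310 h | 29% | 44% |
| 358 h | 13% | 19% |
| 454 h | 2% | 4% |
| 550 h | 0.4% | 0.7% |

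Inhibition does fade inside the sampling window.

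**Effect on the ratio.** The documents do not give the inputs needed, so these are assumptions:
- one compartment, absorption rate 1/h;
- CL(t) = CL0/(1 + (R − 1)·I(t)), with R the fold effect on systemic clearance;
- I = 1 until 238 h or 262 h, then halving every 40 h;
- BI 706321 half-life alone 12 to 64 h, with 38.4 h shown because 192 h / 5 = 38.4 h.

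Shortfall = 1 − (ratio for the course given)/R. Ranges cover the two decay starts.

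| Half-life alone | R = 2 | R = 3 | R = 5 |
|---|---|---|---|
| 12 h | 0% | under 1% | 2-3% |
| 24 h | about 1% | 3-4% | 12-13% |
| 38.4 h | 3-4% | 9-11% | 23-25% |
| 64 h | 9-10% | 20-22% | 37-39% |

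At 38.4 h the ratios themselves are 1.93-1.94, 2.68-2.72 and 3.74-3.85. A second calculation, which sums the individual itraconazole doses instead of using a flat plateau, gives shortfalls of 3%, 10% and 24%.

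**If part of the clearance is not inhibited.** Protocol 1.3 says CYP3A4 is the main route, not the only one. Take CL = CL0·[fm/(1 + P·I) + 1 − fm], with the inhibitable fraction fm set so that full inhibition gives R, that is fm = (1 − 1/R)(1 + P)/P. With P assumed to be 10 to 50 and a half-life of 38.4 h, the shortfall is 1-2%, 5-8% and 16-23% for R = 2, 3 and 5. The same fold effect then needs stronger inhibition of the affected route, which takes longer to wear off.

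**Against the planned precision.** Protocol Table 7.7: 1 illustrates ratios up to 200%. At 2-fold and 38.4 h the gap is a factor of 2/1.93 = 1.04, against a precision factor of 1.21 to 1.33. At 5-fold it is 5/3.74 = 1.34 with fully inhibitable clearance, about the width of the planned interval.

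**The case for a change.** The best case for a change is that the condition is the protocol's own expectation. It foresees a longer terminal half-life under itraconazole, and it cites an 11-fold AUC increase for oral midazolam as a possible scale. Large effects are therefore not excluded, and at 5-fold with a half-life of 38.4 h or more the gap can match or exceed the planned precision. Reporting the share of AUC0-∞ after 262 h would cost little, and fixing the reading in advance avoids a caveat added after the fact.

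The mechanism and direction stand. The 11-fold figure is an oral AUC ratio, so it mixes first-pass and systemic effects, and only the systemic part creates a gap.

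The proposed additions would help little:
- **Share after 262 h.** This is a weak guide to the gap. Across half-lives of 24 to 64 h, a 10% share goes with anything from 2% to 13% understatement. At 64 h the share is already 6% with no interaction at all, so a 5% trigger would fire without cause.
- **Extrapolating from samples up to 262 h.** This avoids the fading phase, but at 38.4 h the extrapolated part reaches 20% of the area at about 3-fold, just where the gap starts to matter. Applying a 20% limit subject by subject would drop the subjects with the largest effects.

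The silence of the visible SAP is also weak evidence of a gap. Its contents list has five redacted entries, one directly after 7.4.1, and non-compartmental rules sit in company standards that are not part of these documents.

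**Conclusion.** No change is needed. The AUC0-∞ ratio is the right estimate for the objective in Protocol 2.1.1, and the model, confidence interval, dosing and sampling raise no error on this point. Reading the ratio as the effect of unending inhibition would be a later interpretation that neither document makes.

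For that other reading, the true ratio is a lower bound, with equality if itraconazole acts only on first pass or if BI 706321 is essentially cleared before itraconazole wears off. With fully inhibitable clearance and assumed half-lives of 12 to 64 h, the shortfall is 0-10% at 2-fold, 0-22% at 3-fold and 2-39% at 5-fold. At 38.4 h with some uninhibited clearance it is 1-2%, 5-8% and 16-23%. These figures rest on linear one-compartment kinetics. They do not model non-linear itraconazole kinetics or separate inhibition by its metabolites. Cmax is not affected.

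If the data show a large effect with much of the area after 262 h, the trial report can say that the ratio applies to the course given and may be a lower bound for maintained inhibition. The planned samples already allow that, and the SAP does not have to be amended first.
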